10.5. Appendix 5: Liver Safety: Suggested Actions and Follow-up Assessments

Hepatic Evaluation Testing

See Section 8.2.5 for guidance on appropriate test selection.

The Lilly-designated central laboratory must complete the analysis of all selected testing except for microbiology testing.

Local testing may be performed *in addition to central testing* when necessary for immediate participant management.

Results will be reported if a validated test or calculation is available.

Hematology	Clinical Chemistry
Hemoglobin	Total bilirubin
Hematocrit	Direct bilirubin
Erythrocytes (RBCs - red blood cells)	Alkaline phosphatase (ALP)
Leukocytes (WBCs - white blood cells)	Alanine aminotransferase (ALT)
Differential:	Aspartate aminotransferase (AST)
Neutrophils, segmented	Gamma-glutamyl transferase (GGT)
Lymphocytes	Creatine kinase (CK)
Monocytes	Other Chemistry
Basophils	Acetaminophen
Eosinophils	Acetaminophen protein adducts
Platelets	Alkaline phosphatase isoenzymes
Cell morphology (RBC and WBC)	Ceruloplasmin
Coagulation	Copper
	Ethyl alcohol (EtOH)
Prothrombin time, INR (PT-INR)	Haptoglobin
Serology	Immunoglobulin IgA (quantitative)
Hepatitis A virus (HAV) testing:	Immunoglobulin IgG (quantitative)
HAV total antibody	Immunoglobulin IgM (quantitative)
HAV IgM antibody	Phosphatidylethanol (PEth)
Hepatitis B virus (HBV) testing:	Urine Chemistry
Hepatitis B surface antigen (HBsAg)	Drug screen
Hepatitis B surface antibody (anti-HBs)	Ethyl glucuronide (EtG)
Hepatitis B core total antibody (anti-HBc)	Other Serology
Hepatitis B core IgM antibody	Anti-nuclear antibody (ANA)

Hepatitis B core IgG antibody	Anti-smooth muscle antibody (ASMA) ^a
HBV DNA ^b	Anti-actin antibody ^c
Hepatitis C virus (HCV) testing:	Epstein-Barr virus (EBV) testing:
HCV antibody	EBV antibody
HCV RNA ^b	EBV DNA ^b
Hepatitis D virus (HDV) testing:	Cytomegalovirus (CMV) testing:
HDV antibody	CMV antibody
Hepatitis E virus (HEV) testing:	CMV DNA ^b
HEV IgG antibody	Herpes simplex virus (HSV) testing:
HEV IgM antibody	HSV (Type 1 and 2) antibody
HEV RNA ^b	HSV (Type 1 and 2) DNA ^b
Microbiology^d	Liver kidney microsomal Type 1 (LKM-1) antibody
Culture:	
Blood	
Urine	

^a Not required if anti-actin antibody is tested.

^b Reflex or confirmation dependent on regulatory requirements, testing availability, or both.

^c Not required if anti-smooth muscle antibody (ASMA) is tested.

^d Assayed ONLY by investigator-designated local laboratory; no central testing available.

10.6. Appendix 6: Medical Device Adverse Events (AEs), Adverse Device Effects (ADEs), Serious Adverse Events (SAEs) and Device Deficiencies: Definition and Procedures for Recording, Evaluating, Follow-up, and Reporting

Refer to Appendix 3 for definitions and procedures for recording, evaluating, follow-up, and reporting of all events.

10.7. Appendix 7: Country-specific Requirements

10.7.1. Canada

This section describes protocol changes applicable to adult participants at study sites in Canada.

This table describes the changes and provides a rationale for the changes.

Protocol Section Number and Name	Description of the Change	Brief Rationale
Inadvertently Enrolled Participants	New section specific to Canada.	Information on inadvertently enrolled participants added per Canadian local requirements.

The revised text described below shows the changes applicable to adult participants at study sites in Canada. Deletions are identified by ~~strike-through format~~ and additions by underlined text.

Inadvertently Enrolled Participants

If the sponsor or investigator identifies a participant who did not meet enrollment criteria and was inadvertently enrolled, then the participant should be discontinued from study intervention and safety follow-up should be performed as outlined in the SoA and Section 8.3 of the protocol.

10.7.2. Brazil

This section describes protocol changes applicable to adult participants at study sites in Brazil.

This table describes the changes and provides a rationale for the changes.

Protocol Section Number and Name	Description of the Change	Brief Rationale
Section 5.2. Exclusion Criteria	Exclusion criterion 28 30 days is changed to 1 year.	Resolution No. 251 (Brazil 1997). The National ERB Brazil recommends not having a participant enter a new clinical study if less than 1 year has elapsed since participation in another clinical study of an investigational drug or device unless there is a direct benefit to the research participant.
Section 10.1.12. Sample Retention	Biological samples will be stored for up to 10 years.	Compliance with Brazilian regulation applicable to sample storage, resolution CNS 441 (Brazil 2011).
Patient Access to Project Benefits	New section specific to Brazil.	Clarifies the sponsor responsibilities to comply with Resolution CNS 466 (Brazil 2012) and RDC 38 (Brazil 2013).
Section 11. References	Addition of Brazil-specific references	The references are specific to the Brazil-specific requirements.

The revised text described below shows the changes applicable to adult participants at study sites in Brazil. Deletions are identified by ~~strikethrough format~~ and additions by underlined text.

5.2. Exclusion Criteria

28. ~~Are currently enrolled or have participated within the last 30 days in a clinical study involving an investigational intervention or any other type of medical research judged not to be scientifically or medically compatible with this study. If the previous investigational intervention has a long half-life, 3 months or 5 half-lives, whichever is longer, should have passed prior to Visit 1.~~

Are currently enrolled in, discontinued, or completed within a period of 1 year, before inclusion, from a clinical study involving an investigational intervention or nonapproved use of a drug or device, or concurrently enrolled in any other type of medical research judged not to be scientifically or medically compatible with this study unless there is direct benefit to the research subject. A time period of 30 days, as indicated by the protocol, must still be followed if a direct benefit to the research participant is identified.

10.1.12. Sample Retention

In Brazil, the biological samples obtained within this study will be stored for up to 10 years, with possibility of renewal under request, followed by appropriate justification and a report with all activities developed with the biological samples (CNS 441/2011). The sample and any data generated from it can be linked back to the participant only by investigator site personnel. The duration allows the sponsor to respond to regulatory requests related to the study intervention.

Patient Access to the Project Benefits

In Brazil, at the end of their participation in the study, all participants must have assured access to the best proven prophylactic, diagnostic, and therapeutic methods, which may include LY3209590 or insulin degludec, identified through the study (CNS 466/2012 and RDC 38/2013).

11. References

BRASIL, MINISTÉRIO DA SAÚDE. Resolução 251/1997 do Conselho Nacional de Saúde/MS: Normas de Pesquisa com Novos Fármacos, Medicamentos, Vacinas e Testes Diagnósticos Envolvendo Seres Humanos.

BRASIL, MINISTÉRIO DA SAÚDE. Resolução 466/2012 do Conselho Nacional da Saúde / MS: Diretrizes e Normas Regulamentadoras de Pesquisas Envolvendo Seres Humanos. Publicado no Diário Oficial da União em 13 de junho, 2013.

BRASIL, MINISTÉRIO DA SAÚDE. Resolução 340/2004 do Conselho Nacional da Saúde/MS: Diretrizes para Análise Ética e Tramitação dos Projetos de Pesquisa da Área Temática Especial de Genética Humana.

BRASIL, MINISTÉRIO DA SAÚDE. Resolução 441/2011 do Conselho Nacional da Saúde / MS: Diretrizes para análise ética de projetos de pesquisas que envolvam armazenamento de material biológico humano ou uso de material armazenado em pesquisas anteriores.

BRASIL, MINISTÉRIO DA SAÚDE. Resolução-RDC 38/2013 da Agência Nacional de Vigilância Sanitária/MS: Aprova o regulamento para os programas de acesso expandido, usocompassivo e fornecimento de medicamento pós-estudo.

10.7.3. Germany

This section describes protocol changes applicable to adult participants at study sites in Germany.

This table describes the changes and provides a rationale for the changes.

Protocol Section Number and Name	Description of the Change	Brief Rationale
7.2. Participant Discontinuation/Withdraw from the Study	Deleted references to “legally authorized representative,” “legal guardian,” “parents”.	The German Drug Law (Arzneimittelgesetz – AMG) with reference to EU Regulation 536/2014 requires that adult participants act on their own behalf and provide their own written informed consent. If written consent is not possible, verbal consent with a witness is acceptable. No legal representative consent is accepted.
10.8 Appendix 8: Provisions for Changes in Study Conduct During Exceptional Circumstances	Replaced references to “exceptional circumstances” with the “COVID-19 pandemic”.	Temporary measures may only be used in response to the COVID-19 pandemic.

The revised text described below shows the changes applicable to adult participants at study sites in Germany. Deletions are identified by ~~strikethrough format~~ and additions by underlined text.

7.2. Participant Discontinuation/Withdraw from the Study

A participant may withdraw from the study:

- at any time at the participant’s own request
- ~~at the request of the participant’s designee (for example, parents or legal guardian)~~
- at the discretion of the investigator for safety, behavioral, compliance, or administrative reasons
- if enrollment in any other clinical study involving an investigational product or enrollment in any other type of medical research judged not to be scientifically or medically compatible with this study
- if the participant, for any reason, requires treatment with another therapeutic agent that has been demonstrated to be effective for treatment of the study indication, discontinuation from the study occurs prior to introduction of the new agent.

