6.1.2. Rescue Medicine for Management of Severe or Persistent Hyperglycemia

If a participant develops severe, persistent hyperglycemia after randomization, optimization of concomitant antihyperglycemic medication and/or the addition of an allowed agent for rescue therapy should be considered after investigator assessment, based on conditions described in this table.

Average of FBG over 2-week period	Timing of events
>270 mg/dL (15 mmol/L)	From Visit 15 until 17 (Week 12 to 16)
>240 mg/dL (13 mmol/L)	After Visit 17 until 19 (Week 16 to 20)
>200 mg/dL (11 mmol/L)	After Visit 19 until 31 (Week 20 to end of study treatment at Week 52)

First, investigators should confirm participant compliance with the assigned intervention and that they do not have an acute condition causing severe hyperglycemia.

Rescue therapy will begin with dose optimization of the participant’s current concomitant antihyperglycemic medications. Then consider the addition of an allowed agent for rescue therapy (see Section 6.8.3), if applicable, so the participant is taking up to 3 antihyperglycemic medications at effective doses before considering prandial insulin rescue therapy.

If severe, persistent hyperglycemia is not improving in spite of compliance with the assigned therapeutic regimen and optimization of other concomitant glucose-lowering agents, the addition of prandial insulin may be considered.

Participants who receive rescue therapy for hyperglycemia management should also continue administering either LY3209590 or insulin degludec for the remaining period in the study.

Participants who require a non-study basal insulin or insulin mixture as rescue therapy must discontinue study basal insulin therapy (LY3209590 or insulin degludec). The participant will remain in the study and follow procedures for the remaining study visits.

The investigator should ensure that the participant met the criteria for severe or persistent hyperglycemia before initiating rescue medicine and document this in the source files.

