7.2. Participant Discontinuation/Withdrawal from the Study

Discontinuation is expected to be uncommon.

A participant may withdraw from the study

- at any time at the participant's own request
- at the request of the participant's designee, for example, parents or legal guardian
- at the discretion of the investigator for safety, behavioral, compliance, or administrative reasons
- if the participant is diagnosed with any type of diabetes mellitus other than T2D
- if enrolled in any other clinical study involving an investigational product, or enrolled in any other type of medical research judged not to be scientifically or medically compatible with this study, and
- if the participant, for any reason, requires treatment with a therapeutic agent that is prohibited by the protocol and has been demonstrated to be effective for treatment of the study indication. In this case, discontinuation from the study occurs prior to introduction of the new agent.

At the time of discontinuing from the study, if possible, the participant will complete procedures for an early discontinuation visit and posttreatment follow-up, as shown in the SoA.

If the participant has not already discontinued the study intervention, the participant will be permanently discontinued from the study intervention at the time of the decision to discontinue the study.

If the participant withdraws consent for disclosure of future information, the sponsor may retain and continue to use any data collected before such a withdrawal of consent.

If a participant withdraws from the study, the participant may request destruction of any samples taken and not tested, and the investigator must document this in the site study records.

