8.3. Adverse Events, Serious Adverse Events, and Product Complaints

The definitions of the following events can be found in Appendix 3:

- Adverse events (AEs)
- Serious adverse events (SAEs)
- Product complaints (PCs)

These events will be reported by the participant (or, when appropriate, by a caregiver, surrogate, ~~or the participant's legally authorized representative~~).

Section 10.8. Appendix 8: Provisions for Changes in Study Conduct During Exceptional Circumstances due to the COVID-19 Pandemic

Implementation of this appendix

The changes to procedures described in this appendix are temporary measures intended to be used only during specific time periods as directed by the sponsor in partnership with the investigator.

Exceptional circumstances Study disruptions due to the COVID-19 pandemic

~~Individual, site, or regional restrictions due to the COVID-19 pandemic~~ **Exceptional circumstances** are rare events that may cause disruptions to the conduct of the study. ~~Examples include pandemics or natural disasters~~. These disruptions may limit the ability of the investigators, participants, or both to attend on-site visits or to conduct planned study procedures.

Implementing changes under exceptional circumstances during the COVID-19 pandemic

~~In an exceptional circumstance, a~~ After receiving the sponsor's written approval, sites may implement changes if permitted by local regulations.

After approval by local ERBs, regulatory bodies, and any other relevant local authorities, implementation of these ~~exceptional circumstance~~ changes will not typically require additional notification to these groups, unless they have specific requirements in which notification is required, for example, upon implementation and suspension of changes. All approvals and notifications must be retained in the study records.

If the sponsor grants written approval for changes in study conduct, the sponsor will also provide additional written guidance, if needed.

Considerations for making a change

The prevailing consideration for making a change is ensuring the safety of study participants. Additional important considerations for making a change are compliance with GCP, enabling participants to continue safely in the study and maintaining the integrity of the study.

Informed consent

Additional consent from the participant will be obtained, if required, for

- participation in remote visits, as defined in Section "Remote Visits"

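### The German version of Section 7.2 drops the limit to prohibited agents, so read literally a German participant who needs permitted rescue therapy must leave the study first

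*Protocol*

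**What the plan says.** Main Protocol 7.2 lists reasons why a participant may withdraw. One is that the participant "requires treatment with a therapeutic agent that is prohibited by the protocol" and the agent is effective for the indication; in that case the participant leaves the study before the agent starts. Another is "if the participant is diagnosed with any type of diabetes mellitus other than T2D".

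The German replacement for 7.2, in Protocol 10.7.3, words the first of these differently. It applies when the participant "requires treatment with another therapeutic agent that has been demonstrated to be effective for treatment of the study indication", and continues: "discontinuation from the study occurs prior to introduction of the new agent". It does not mention prohibited agents. The bullet on other types of diabetes does not appear at all.

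The German change table gives one change for 7.2, the removal of references to representatives, guardians and parents. The rationale concerns consent only: "No legal representative consent is accepted". The section states that deletions are shown by strikethrough.

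Protocol 6.1.2 starts rescue with dose optimization of current medicines. It goes on: "Then consider the addition of an allowed agent for rescue therapy", and after that prandial insulin may be added. It also says: "Participants who receive rescue therapy for hyperglycemia management should also continue administering either LY3209590 or insulin degludec for the remaining period in the study". Protocol 6.8.3 tabulates which drug classes may be used as rescue. Its note keeps participants in the study even when they must stop study insulin for a non-study basal insulin or a mixture. No German change is shown for 6.1.2, 6.8.3 or 7.1.

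**The concern.** The two versions of 7.2 give different rules for the same event. Under main 7.2, a participant who needs a permitted rescue agent stays. Under the German wording, needing any further effective glucose-lowering agent is a reason to leave, and leaving comes before the agent is given. A German site would hold this text alongside 6.1.2 and 6.8.3, which tell it to keep the same participant in the study.

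What is at stake is the Week 52 HbA1c for the US treatment regimen estimand. Protocol Section 3 defines that estimand regardless of treatment discontinuation and rescue. SAP 1.2 says HbA1c collection continues after study insulin stops. A participant withdrawn under the German bullet has no Week 52 value, and SAP 4.3.2 would impute it. The imputation draws on retrieved dropouts, who by definition stopped study insulin. Yet most rescued participants would have continued it under 6.1.2. Safety observation would also be cut short, although the safety set is meant to include data after rescue. The efficacy estimand is not affected, because it excludes data after rescue by design.

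**Working it through.** **1. Text comparison**

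| Item | Main 7.2 | German 7.2 |
|---|---|---|
| Trigger | Effective agent that the protocol prohibits | Any other effective agent |
| Consequence | Leaves study before the agent starts | Same |
| Diabetes other than T2D | Listed | Absent, unmarked |
| Request by a designee | Listed | Struck through, as the change table declares |

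Only the last row is accounted for by the change table and the strikethrough convention.

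**2. How far the German bullet conflicts with 6.8.3**

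The rescue column covers 11 drug classes:
- allowed: 7 (GLP-1 RAs, DPP-4 inhibitors, SGLT2 inhibitors, prandial insulin, alpha-glucosidase inhibitors, sulfonylureas, thiazolidinediones)
- allowed conditionally: 1 (metformin, if below the maximum approved dose)
- covered by the note that the participant remains in the study: 2 (non-study basal insulins, insulin mixtures)
- not allowed: 1 (meglitinides)

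So 7 + 1 + 2 = 10 of 11 classes at most. If the metformin entry means only raising an existing dose, the count is 9, because a dose increase of a current medicine adds no new agent.

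**3. Number of participants (assumed shares)**

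German enrolment and the rescue rate are not stated. Assume Germany supplies 2% to 10% of the 888 randomized, and 2% to 10% of those need an added agent.
- Low: 888 × 0.02 × 0.02 = 0.36
- High: 888 × 0.10 × 0.10 = 8.88

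**4. Effect on an arm mean**

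Each arm has 888 / 2 = 444 participants. Assume that all affected participants are in one arm and that the imputed change is wrong by 0.5 to 1.5 HbA1c points, always in the same direction.
- Low: 0.36 × 0.5 / 444 = 0.0004 points
- High: 8.88 × 1.5 / 444 = 0.030 points

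The noninferiority margins are 0.3 and 0.4. If the losses were balanced between arms, the shift in the difference would be near zero.

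**5. Effect on power**

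Power = Φ(margin / (SD × √(2/n)) − 1.96), with no true difference, SD 1.1 and margin 0.3.
- Plan's case, n = 377 per arm: standard error 1.1 × √(2/377) = 0.0801; 0.3 / 0.0801 − 1.96 = 1.78; power 96.3%. This agrees with the plan's statement of at least 95%.
- With 9 fewer per arm, n = 368: standard error 0.0811; 0.3 / 0.0811 − 1.96 = 1.74; power 95.9%.

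Nine per arm is 18 in total, about twice the upper figure in step 3, so this overstates the loss.

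**The case against.** The strongest reply is that the German text is an unintended paste of older wording. Under the section's own convention, an unmarked omission is not a deletion. On that view the main-text limit still applies, and investigators would turn to 6.1.2 and 6.8.3 for a rescue case. The list also opens permissively, as reasons why a participant may withdraw.

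The omission may well be unintended, and intent cannot be established from the documents. Underlining is not visible in the text as read. The change table is not a complete record either: the German 8.3 text, which begins "These events will be reported by the participant (or, when appropriate, by a caregiver, surrogate", strikes out the representative wording without being listed there. But a pasted error in operative text is still an error. The permissive opening does not cancel the end of the bullet, which fixes the order of events: study discontinuation first, new agent second. At best the site has two incompatible instructions.

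Some narrower points stand. Protocol 7.1 and the SAP 1.2 sentence concern participants who permanently stop study insulin, so for most rescued participants the direct conflict is with 6.1.2 and 6.8.3. A count of classes says nothing about how often each is used, and rescue starts with dose optimization, which the German bullet does not touch. No consequence is shown for the missing bullet on other types of diabetes, since investigator discretion remains in the German list.

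**Conclusion.** The concern holds. The German 7.2 text is wrong as written: it sends out of the study participants whom 6.1.2 and 6.8.3 keep in it, for 9 or 10 of the 11 tabulated drug classes. The severity is minor. Only German sites and added agents are involved, and only the treatment regimen estimand and safety follow-up are touched. Under the assumed shares, 0.4 to 8.9 participants are affected and one arm's mean moves by at most about 0.03 points, so the primary conclusion is not threatened. Those figures rest on assumed values for the German share, the rescue rate and the imputation error. The reason to correct the text is the conflicting instruction, which does not depend on them.

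**What to change.** Align the German 7.2 list with current main 7.2, so that only the representative wording differs. Restore the limit to agents prohibited by the protocol (six words) and the bullet on diabetes other than T2D. Optionally, add a cross-reference stating that agents permitted under 6.1.2, 6.8.3 and 7.1 do not count as prohibited for this bullet. The sponsor's rule for agents that really are prohibited stays unchanged.

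The cost is a wording correction in one country section, with no new visits or data. Under Protocol 10.1.1 an amendment may need ethics committee approval, so the correction can go with the next amendment.
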